Trial design: Open label, single cohort proof of concept trial. An additional arm of the study will be for subjects treated with the study drug in malignant pituitary tumors. Three clinical trial sites, one at CSMC and the others at Johns Hopkins Hospital and Massachusetts General Hospital.

Study population: Patients will be recruited from the Pituitary Center at Cedars-Sinai Medical Center and the other two sites.

Intervention: lapatinib 1250 mg daily for 6 months. Patients will be treated with the standardized dose used in breast cancer therapy for six months (Cameron & Stein 2008; Geyer et al. 2006). The drug will be supplied by Novartis Oncology.

- a. Primary outcome variable.

Primary outcome in nonfunctioning pituitary adenomas: 40% reduction in tumor size in any dimension. Tumor size and volume will be calculated using Open Source OsiriX® Imaging Software for MacOS. MRIs will be performed at baseline and at 3 and 6 months All MRIs will be centrally read by the dedicated pituitary radiologist at CSMC.

Primary outcome in prolactinomas: 40% reduction in tumor size in any dimension.

Primary outcome in malignant pituitary tumors: Progression free survival

- b. Secondary outcome variables.

Secondary outcomes in prolactinomas:

(a) achievement of 50% reduction of PRL levels (b) PRL normalization (c) percent reduction in PRL levels (d) percent reduction in tumor volume. Tumor volume will be calculated using Open Source OsiriX® Imaging Software for MacOS. (e) correlation of tumor size and PRL reduction (f) clinical predictors of TKI response, including age, gender, duration of disease, dose and duration of dopamine agonist therapy, baseline PRL, and baseline tumor size.

Secondary outcomes in malignant pituitary tumors: partial response, complete response, mortality, 24 hour urine free cortisol levels for Cushing carcinomas, IGF-1 levels for acromegaly carcinomas.

We will correlate ErbB receptor expression with the subjects' clinical response to the study drug. This will be performed through immunohistochemistry staining of pituitary tumor slides from surgery.

Section 5.0. Selection and Withdrawal of Subjects

Inclusion criteria: Subjects with non-functioning pituitary adenomas, who have undergone at least one prior surgical resection and have demonstrated recurrence on MRI.

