Patients should be instructed to notify the investigator if it is determined after completion of the study that they become pregnant either during the treatment phase of the study or within five days after the treatment period.

Whenever possible a pregnancy should be followed to term, any premature termination reported, and the status of the mother and child should be reported to GlaxoSmithKline after delivery.

Section 9.0.

Statistics

Sample size calculation for prolactinomas: Sample size was computed using proportions as standard deviation for tumor reduction on the study drug was unknown. While for the data analysis we will use quantitative analysis using the Hotelling’s T², using binary data for power calculations would be inefficient as this would require a larger sample size. We could not use the quantitative analysis for power calculations, however, as we do not know the variance.

The primary outcome is a reduction in maximal size of resistant tumors. Stabilization is defined as <20% reduction in any dimension on MRI by RECIST criteria. MRIs will be performed at baseline and at 3 and 6 months.

The null hypothesis is H₀: no reduction P<0.20 vs. the alternative hypothesis H_a: P>0.40. This will give an effect size of 0.20 to detect. Exact confidence interval and significance test is obtained from the binomial distribution. The reduction is for resistant prolactinomas (Di Sarno, 2001; Delgrange, 2009). Power is >80%, using one tailed

CSMC Office of Research Compliance

Reference: [ICH E6: Good Clinical Practice: Consolidated Guidance](#)

RECOMMENDED ELEMENTS OF A SCIENTIFIC PROTOCOL
(Noted sections should only be included as applicable to your research)

hypothesis, alpha of 0.10. This gives a target sample size of 24 subjects to achieve this power.

Sample size: use one-sided exact test. $H_0: p = p_0$; $H_A: p > p_0$.

Power	alpha	P_0 : null proportion	P_1 : true proportion	N
80%	0.05	20%	30%	116
80%	0.10	20%	30%	88
80%	0.05	20%	35%	56
80%	0.10	20%	35%	44
80%	0.05	20%	40%	35
80%	0.10	20%	40%	24

Secondary MRI studies will deal with various aspects and location by MRI of these tumors. Secondary PRL statistical studies will also be carried out under secondary outcomes.

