Tumor maximal size will be obtained at baseline, 3 months, 6 months after initiation of treatment. The primary hypothesis is the change from baseline to 6 months. The analysis using maximal resistant tumor size will be carried out for the specified times given above. Initially this will be by descriptive analytic and then by inferential analysis using the test for change between baseline and 6 months and change between baseline and 3 months using rank test. We will also use Hotelling's T^2 to combine both pre-post changes.

This study is in the clinical trials paradigm essentially a Phase IIa trial and thus use of alpha type 1 error is at 10%. This is sanctioned by the biostatistics section of NCI.⁴⁰ We will also analyze the secondary endpoints of Aim 1 according to the above models. Concepts behind analysis for quantitative and binary are the same though the methods are different.

Our overall target sample size is 30 subjects which includes nonfunctioning adenomas and prolactinomas, 15 to be recruited from Cedars Sinai Medical Center and 15 from Johns Hopkins Hospital and Massachusetts General Hospital. We aim to recruit 24 subjects with prolactinomas and 6 nonfunctioning adenomas.

Due to the rarity of pituitary tumors in the general population and even more rare are aggressive pituitary tumors such as we propose to study, it is difficult to do a randomized placebo controlled trial with sufficient sample size numbers to achieve adequate power. By using the subjects as their own controls, we alleviate the issues with recruitment. This is a safety and activity trial to look for a sufficient effect of the drug on tumor growth before proceeding to a larger, randomized placebo controlled trial.

Section 10.0. Quality Control and Quality Assurance

Only samples and data collected with appropriate consent will be used for the proposed analysis. Specimens and data collected under the proof of concept clinical trial of lapatinib will be coded in such a way so that other members of the research team will be unable to ascertain the identity of specific patients. All of our data will be

RECOMMENDED ELEMENTS OF A SCIENTIFIC PROTOCOL
(Noted sections should only be included as applicable to your research)

38

maintained confidentially. Data will be kept in locked file cabinets and in password protected files on computer systems.

Section 11.0 Ethical considerations relating to the trial

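### The prolactinoma primary outcome differs between Sections 4.0/7.0 and Section 9.0; the binomial test behind N = 24 does not name its event, and no deciding test is designated

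*Combined protocol and SAP*

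**What the plan says.** **Sections 4.0 and 7.0** use the same sentence: "Primary outcome in prolactinomas: 40% reduction in tumor size in any dimension". This is a binary outcome. It can be met on any axis, and although MRIs are listed at 3 and 6 months, neither section says which one counts.

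**Section 9.0**, under the prolactinoma sample size, says "The primary outcome is a reduction in maximal size of resistant tumors". It gives no response threshold and does not refer back to Sections 4.0 or 7.0. It continues with "Tumor maximal size will be obtained at baseline, 3 months, 6 months after initiation of treatment" and "The primary hypothesis is the change from baseline to 6 months".

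**Sizing, Section 9.0.** The hypotheses are labelled "no reduction P<0.20 vs. the alternative hypothesis" of P above 0.40, one-tailed, alpha 0.10, giving 24 subjects. The section adds that the reduction relates to resistant prolactinomas and cites two studies. It does not describe what a patient must show to be counted in P.

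**Tests, Section 9.0.** Three are mentioned:
- the binomial: "Exact confidence interval and significance test is obtained from the binomial distribution";
- Hotelling's T², named in the sizing paragraph as the method of data analysis and mentioned again later as an additional way of combining the two changes;
- a rank test of the changes to 6 months and to 3 months.

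The section explains why sizing and analysis differ: "Sample size was computed using proportions as standard deviation for tumor reduction on the study drug was unknown".

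**The concern.** The outcome in Sections 4.0 and 7.0 differs from that in Section 9.0 in two ways. The measure differs (any axis against maximal size), and so does the type (responder yes/no against quantitative change). A tumour can lose 40% of a shorter axis while its longest axis is unchanged. A tumour can also shrink measurably without coming near 40%.

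The only stated power belongs to a binomial test whose event is not written down, while the described analysis is quantitative. The trial is open label with no control group, and its purpose is to decide whether a larger randomised placebo-controlled trial is justified. In that setting a single pre-specified rule is the main protection against choosing the analysis after seeing the data. As written, two analysts following different sections could reach opposite verdicts on the same scans.

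**Working it through.** **Inputs (Section 9.0):** p0 = 0.20, p1 = 0.40, one-sided alpha 0.10, target power 80%, N = 24.

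**Step 1: reproduce the plan's figure.** For X ~ Binomial(24, p), the tail is P(X ≥ r) = Σ C(24,k) p^k (1−p)^(24−k), summed from k = r to 24.
- r = 7: P(X ≥ 7 | 0.20) = 0.1889, above 0.10, so 7 responders are not enough.
- r = 8: P(X ≥ 8 | 0.20) = 0.0892, at or below 0.10, so the cut-off is 8.
- Power: P(X ≥ 8 | 0.40) = 0.8081.

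The same rule at n = 20, 21, 22 and 23 gives power 0.7500, 0.6505, 0.7102 and 0.7627, so 24 is the smallest n that reaches 80%. All six rows of the protocol's table (116, 88, 56, 44, 35, 24) reproduce as the smallest such n. The arithmetic is sound.

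**Step 2: what does P count?**

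| Place | Measure | Threshold | Time point |
|---|---|---|---|
| Sections 4.0, 7.0 | any dimension | 40% | not stated (MRI at 3 and 6 months) |
| Section 9.0, primary outcome and hypothesis | maximal size | none | 6 months |
| Section 9.0, binomial hypotheses | not stated | not stated | not stated |

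The third row produced N = 24, and nothing in the text ties it to either of the other two.

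**Step 3: does the stated power carry over to the quantitative tests?** The nulls differ:
- binomial: the proportion of responders is at most 0.20;
- rank test (read here as a signed-rank test on within-patient change, since the type is not given): changes are centred on zero;
- Hotelling's T²: the mean changes at 3 and 6 months are both zero. It also has no direction, whereas the sizing is one-tailed.

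**Step 4: illustration (constructed, not trial data; no SD assumed).** Let the 24 tumours shrink by 1%, 2%, …, 24%.
- Signed-rank: every change is a reduction, so W+ = 24 × 25 / 2 = 300, its maximum. One-sided exact p = 1 / 2^24 = 6.0e-8.
- Binomial on 40% responders: 0 of 24, p = P(X ≥ 0 | 0.20) = 1.0.

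The rank test is overwhelmingly positive and the responder test is as negative as it can be. Power computed for one therefore says nothing about the other.

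**The case against.** **The mismatch is disclosed.** Section 9.0 says it sized on proportions because the variance was unknown, and it regards this as the costlier route: "using binary data for power calculations would be inefficient as this would require a larger sample size". A reader could take N = 24 as conservative for the quantitative analysis. The explanation stands as an account of how N was chosen. It does not reconcile the two outcomes, name the event or choose the test. A reader might conversely infer that the trial is underpowered for the rank test. The documents do not support that either: they give no variance, and in the illustration the rank test is the more sensitive. The point is only that the power above 80% is not a statement about that test.

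**The event may be traceable.** A reader might infer that the 20% and 40% rates cannot be checked at all. That goes too far, because Section 9.0 ties the reduction to resistant prolactinomas and cites two studies that may define it. The supportable statement is that the protocol text does not restate the event. The 40% responder of Sections 4.0 and 7.0 is the natural guess, but Section 9.0 states a different primary outcome, so it remains a guess.

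**The tests have an implied order.** The 6-month time point is fixed for the primary hypothesis, a rank test is named for that change, and the later mention of Hotelling's T² is introduced with *also*, which suggests a supporting role. This narrows the ambiguity without closing it: the sizing paragraph names Hotelling's T² as the data analysis, and the same section says the significance test is binomial.

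**N is not wrong.** A reader might infer a sample-size error. There is none: every row of the table reproduces.

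**Conclusion.** The concern holds. The prolactinoma primary outcome is stated in two incompatible ways. The binomial test that gives N = 24 has no stated event, and the deciding test is not settled among the binomial, the rank test and Hotelling's T².

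The stated size and power are correct for the binomial test alone (8 or more of 24, alpha 0.0892, power 0.8081) and do not transfer to the quantitative tests. As to size, the same 24 scans can give p = 6.0e-8 on one analysis and p = 1.0 on another. That is a constructed pattern showing that the verdict can turn on the choice; it is not an estimate of how often it would.

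The conclusion rests on reading the 40% outcome as a reduction of at least 40% and the rank test as a signed-rank test. It needs no assumption about variance or about the true response rate, neither of which the documents give.

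**What to change.** 1. Use one responder definition in Sections 4.0, 7.0 and 9.0, stating the measure (any dimension or maximal diameter, used consistently), the 40% threshold, and the centrally read 6-month MRI.
2. In Section 9.0, state that P is the proportion of treated prolactinoma patients who meet that definition. Confirm from the two cited studies that 20% and 40% refer to that event. If they do not, restate the power.
3. Name one primary test. The exact binomial matches the stated N and power: success at 8 or more if 24 are treated, with the rank test and Hotelling's T² supportive. Recompute the cut-off for the number actually treated. At 23 it stays at 8 (alpha 0.0715, power 0.7627); at 25 it becomes 9 (alpha 0.0468, power 0.7265).
4. If a quantitative test is kept as primary, name it and state that the power above 80% does not apply to it.

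**Cost:** wording only, since the scans, central reading and size measurements are already planned. With the binomial test primary, N stays at 24 if the rates fit the chosen event. The downside is that the stated power may have to be restated if they do not.
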